12.4 STUDY MONITORING, AUDITING, AND INSPECTING

The investigator will permit study-related monitoring, quality audits, and inspections by government regulatory authorities, the Sponsor or its representative(s) of all study-related documents (e.g., source documents, regulatory documents, data collection instruments, case report forms). The investigator will ensure the capability for inspections of applicable study-related facilities. The investigator will ensure that the study monitor or any other compliance or QA reviewer is given access to all study-related documents and study-related facilities.

Participation as an investigator in this study implies the acceptance of potential inspection by government regulatory authorities and the sponsor or its representative(s).

At the Sponsor's discretion, Source Document Verification (SDV) may be performed on all data items or a percentage thereof.

12.5 QUALITY ASSURANCE AND QUALITY CONTROL

In addition to the Clinical Monitoring component of this protocol, the Sponsor's Quality Assurance (QA) department shall establish an Auditing Plan document separate from the protocol to establish the criteria by which independent auditing shall be conducted during the conduct of the study to assess compliance with GCP and applicable regulatory requirements. Data or documentation audited shall be assessed for compliance to the protocol, accuracy in relation to source documents and compliance to applicable regulations.

Each study site shall be required to have Standard Operating Procedures (SOP's) to define and ensure quality assurance/control processes for study conduct, data generation & collection, recording of data/documentation and reporting according to the protocol, GCP and any applicable local, national or international regulations.

Accurate and reliable data collection will be ensured by verification and cross check of the eCRFs against the investigator's records by the study monitor (source document verification) and by the maintenance of a drug-dispensing log by the investigator. Collected data will be entered into a computer database and subject to electronic and manual quality assurance procedures.

12.6 DISCLOSURE AND PUBLICATION POLICY

All information provided regarding the study, as well as all information collected/documenting during the course of the study, will be regarded as confidential. The Sponsor reserves the right to release literature publications based on the results of the study.

A clinical study report will be prepared upon completion of the study. The Sponsor will disclose the study results, in the form of a clinical study report synopsis, to the IEC and the applicable regulatory authorities within one year of the end of the study. The format of this synopsis and that of the clinical study report and its addendum will comply with ICH E3 guidelines for structure and content of a clinical study report.

The financial disclosure information will be provided to the Sponsor prior to study participation from all PIs and Sub-Investigators who are involved in the study and named on the FDA 1572 form.

By conducting this study, the Investigator affirms to the Sponsor that he or she will maintain, in strict confidence, information furnished by the Sponsor including data generated from this study and preliminary laboratory results, except as exempted for regulatory purposes.

All data generated during the conduct of this study is owned by the Sponsor and may not be used by the Investigator or affiliates without the expressed written consent of the Sponsor.

All manuscripts, abstracts, or other presentation materials generated by site investigators must be reviewed and approved by the Sponsor prior to submission.

14 APPENDIX A –CRITERIA FOR RESPONSE ASSESSMENT

Revised Response Criteria for Non- Hodgkin's Lymphoma (Cheson et. al. 2014 Lugano Classification)

Response and Site	PET-CT-Based Response	CT-Based Response
Complete Response		
Lymph nodes and extra-lymphatic sites	
Score 1, 2, or 3* with or without a residual mass on 5PS[†]
 
It is recognized that in Waldeyer's ring or extra-nodal sites with high physiologic uptake or with activation within spleen or marrow (eg, with chemotherapy or myeloid colony-stimulating factors), uptake may be greater than normal mediastinum and/or liver. In this circumstance, complete metabolic response may be inferred if uptake at sites of initial involvement is no greater than surrounding normal tissue even if the tissue has high physiologic uptake
	
Target nodes/nodal masses must regress to ≤ 1.5 cm in LD_i
 
No extra-lymphatic sites of disease

Non- measured lesion	Not applicable	Absent
Organ enlargement	Not applicable	Regress to normal
New lesions	None	None
Bone marrow	No evidence of FDG-avid disease in marrow	Normal by morphology; if indeterminate, IHC negative
Partial Response		
Lymph nodes and extra-lymphatic sites	
Score 4 or 5[†] with reduced uptake compared with baseline and residual mass(es) of any size
 
At interim, these findings suggest responding disease
 
At end of treatment, these findings indicate residual disease
	
$\geq 50\%$ decrease in SPD of up to 6 target measurable nodes and extra-nodal sites
 
When a lesion is too small to measure on CT, assign 5 mm \times 5 mm as the default value
 
When no longer visible, 0 \times 0 mm

		For a node $> 5 \text{ mm} \times 5 \text{ mm}$, but smaller than normal, use actual measurement for calculation
Non- measured lesion	Not applicable	Absent/normal, regressed, but no increase
Organ enlargement	Not applicable	Spleen must have regressed by $> 50\%$ in length beyond normal
New lesions	None	None
Bone marrow	Residual uptake higher than uptake in normal marrow but reduced compared with baseline (diffuse uptake compatible with reactive changes from chemotherapy allowed). If there are persistent focal changes in the marrow in the context of a nodal response, consideration should be given to further evaluation with MRI or biopsy or an interval scan	Not applicable
No response or stable disease		
Target nodes/nodal masses, extra-nodal lesions	Score 4 or 5 with no significant change in FDG uptake from baseline at interim or end of treatment	$< 50\%$ decrease from baseline in SPD of up to 6 dominant, measurable nodes and extra-nodal sites; no criteria for progressive disease are met
Non-measured lesions	Not applicable	No increase consistent with progression
Organ enlargement	Not applicable	No increase consistent with progression
New lesions	None	None
Bone marrow	No change from baseline	Not applicable
Progressive disease		
Individual target nodes/nodal masses, Extra-nodal lesions	Score 4 or 5 with an increase in intensity of uptake from baseline and/or new FDG-avid foci consistent with lymphoma at	PPD Progression: An individual node/lesion must be abnormal with: - LD _i $> 1.5 \text{ cm}$ - Increase by $\geq 50\%$ from PPD nadir.

	interim or end-of-treatment assessment	An increase in LDi or SDi from nadir - 0.5 cm for lesions \leq 2 cm - 1.0 cm for lesions $>$ 2 cm In the setting of splenomegaly, the splenic length must increase by $>$ 50% of the extent of its prior increase beyond baseline (eg, a 15-cm spleen must increase to $>$ 16 cm). If no prior splenomegaly, must increase by at least 2 cm from baseline. New or recurrent splenomegaly.
Non-measured lesions	None	New or clear progression of preexisting non-measured lesions
New lesions	New FDG-avid foci consistent with lymphoma rather than another etiology (eg, infection, inflammation). If uncertain regarding etiology of new lesions, biopsy or interval scan may be considered	Regrowth of previously resolved lesions A new node $>$ 1.5 cm in any axis A new extra-nodal site $>$ 1.0 cm in any axis; if $<$ 1.0 cm in any axis, its presence must be unequivocal and must be attributable to lymphoma Assessable disease of any size unequivocally attributable to lymphoma
Bone marrow	New or recurrent FDG-avid foci	New or recurrent involvement

Abbreviations: 5PS, 5-point scale; CT, computed tomography; FDG, fluorodeoxyglucose; IHC, immunohistochemistry; LDi, longest transverse diameter of a lesion; MRI, magnetic resonance imaging; PET, positron emission tomography; PPD, cross product of the LDi and perpendicular diameter; SDi, shortest axis perpendicular to the LDi; SPD, sum of the product of the perpendicular diameters for multiple lesions.*A score of 3 in many patients indicates a good prognosis with standard treatment, especially if at the time of an interim scan. However, in trials involving PET where de-escalation is investigated, it may be preferable to consider a score of 3 as inadequate response (to avoid undertreatment). Measured dominant lesions: Up to six of the largest dominant nodes, nodal masses, and extra-nodal lesions selected to be clearly measurable in two diameters. Nodes should preferably be from disparate regions of the body and should include, where applicable, mediastinal and retroperitoneal areas. Non-nodal lesions include those in solid organs (eg, liver, spleen, kidneys, lungs), GI involvement, cutaneous lesions, or those noted on palpation. Non-measured lesions: Any disease not selected as measured, dominant disease and truly assessable disease should be considered not measured. These sites include any nodes, nodal masses, and extra-nodal sites not selected as dominant or measurable or that do not meet the requirements for measurability but are still considered abnormal, as well as truly assessable disease, which is any site of suspected disease that would be difficult to follow quantitatively with measurement, including pleural effusions, ascites, bone lesions, leptomeningeal disease, abdominal masses, and other lesions that cannot be confirmed and followed by imaging. In Waldeyer's ring or in extra-nodal sites (eg, GI

tract, liver, bone marrow), FDG uptake may be greater than in the mediastinum with complete metabolic response, but should be no higher than surrounding normal physiologic uptake (eg, with marrow activation as a result of chemotherapy or myeloid growth factors).[†]PET 5PS: 1, no uptake above background; 2, uptake \leq mediastinum; 3, uptake $>$ mediastinum but \leq liver; 4, uptake moderately $>$ liver; 5, uptake markedly higher than liver and/or new lesions; X, new areas of uptake unlikely to be related to lymphoma

Consensus-based uniform response criteria for WM developed by the IWWM, updated in the sixth IWWM

Complete response (CR)	Absence of serum monoclonal IgM protein by immunofixation. Normal serum IgM level. Complete resolution of extramedullary disease, i.e., lymphadenopathy and splenomegaly if present at baseline. Morphologically normal bone marrow aspirate and trephine biopsy
Very good partial response (VGPR)	Monoclonal IgM protein is detectable $\geq 90\%$ reduction in serum IgM level from baseline Complete resolution of extramedullary disease, i.e., lymphadenopathy/splenomegaly if present at baseline. No new signs or symptoms of active disease
Partial response (PR)	Monoclonal IgM protein is detectable $\geq 50\%$ but $< 90\%$ reduction in serum IgM level from baseline. Reduction in extramedullary disease, i.e., lymphadenopathy/splenomegaly if present at baseline. No new signs or symptoms of active disease
Minor response (MR)	Monoclonal IgM protein is detectable $\geq 25\%$ but $< 50\%$ reduction in serum IgM level from baseline No new signs or symptoms of active disease
Stable disease	Monoclonal IgM protein is detectable $< 25\%$ reduction and $< 25\%$ increase in serum IgM level from baseline No progression in extramedullary disease, i.e., lymphadenopathy/splenomegaly No new signs or symptoms of active disease
Progressive disease	$\geq 25\%$ increase in serum IgM level* [†] from lowest nadir (requires confirmation) and/or progression in clinical features attributable the disease

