3.1 INCLUSION CRITERIA

Patients must meet all of the following inclusion criteria to be eligible for participation in this study:

1. Histologically confirmed diagnosis of B-cell non-follicular indolent non-Hodgkin's lymphoma meeting following requirements.
 - a. World Health Organization 2008 classification criteria warranting therapy as per investigator discretion for histologies limited to splenic marginal zone lymphoma (SMZL), nodal marginal zone Lymphoma (NMZL), or extra-nodal marginal zone lymphoma (ENMZL), and lymphoplasmacytic lymphoma.
 - b. Presence of CD20⁺ lymphoplasmacytic lymphoma involving the bone marrow, positive serum immunofixation for monoclonal IgM and atleast one criteria for initiation of treatment as per Consensus panel of International Workshops on Waldenstrom's macroglobulinemia.
2. Relapsed or refractory after at least one prior treatment regimen, with no limit on prior therapies.
3. At least 1 measurable disease lesion >1.5 cm in at least one diameter by CT/CT-PET or magnetic resonance imaging (MRI) in an area of no prior radiation therapy, or in an area that was previously irradiated that has documented progression.
 - a. Exceptions include for Waldenstrom's macroglobulinemia patients without nodal involvement.
4. Waldenstrom's macroglobulinemia patients must have measurable quantitative IgM monoclonal protein greater than normal value.
5. Adequate organ system function, defined as follows:
 - a. Absolute neutrophil count (ANC) \geq 1,000 / platelet count \geq 50,000.
 - b. Total bilirubin \leq 1.5 times the upper limit of normal (ULN)
 - c. Alanine aminotransferase (ALT) and aspartate aminotransferase (AST) \leq 2.5 x ULN if no liver involvement or \leq 5 x the ULN if known liver involvement
 - d. Calculated creatinine clearance >30 mL/min (as calculated by the Cockcroft-Gault or MDRD formula, 24- hour urine Cr clearance also acceptable)
6. ECOG performance status \leq 2
7. Male or female \geq 18 years of age
8. Ability to swallow and retain oral medication
9. Female patients who are not of child-bearing potential and female patients of child-bearing potential who have a negative serum pregnancy test within 3 days prior to Cycle 1, Day 1.
10. Willingness and ability to comply with trial and follow-up procedures, and give written informed consent

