5 STUDY ASSESSMENTS AND TREATMENT SCHEDULE

5.1 STUDY ASSESSMENTS AND TREATMENT SCHEDULE

Cycle = 28 days	Screen	Cycle 1 ₁			Cycles 2-6 ₂					> Cycle 6 ₃		End of Study	Follow-up
					C2	C3	C4	C5	C6	Every 3 Months			
Procedure\Days	-28-0	D1	D8	D15	Day 1					Day 1			Day 1
Medical History	X												
ECOG Performance Status	X	X			X	X	X	X	X	X	X	X	
Physical Examination ₄	X	X			X	X	X	X	X	X	X	X	
Vital Signs (pulse, BP, temp, weight)	X	X	X	X	X	X	X	X	X	X	X	X	
BM Aspirate/Biopsy ₅	X												
12-lead EKG	X												
Tumor Evaluation ₆	X				Every 3 cycles								
Serology: HCV, HBV, CMV ₇	X												
Hematology ₈	X	X	X	X	X	X	X	X	X	X	X	X	
Serum Chemistry	X	X	X	X	X	X	X	X	X	X	X	X	
PT/INR	X				As clinically warranted								
Serum Pregnancy Test ₉	X												
Concomitant Medications	X	X	X	X	X	X	X	X	X	X	X	X	
AE Evaluation ₁₀	X	X	X	X	X	X	X	X	X	X	X	X	
LTFU ₁₁												X	
TGR-1202					Administered orally daily with food								

¹ Treatment Administration +/- 1 day window. Physical Exam, Vital Signs, ECOG PS, Hematology and Serum Chemistry visit days have - 1 day window

² Treatment Administration +/- 3 day window. Physical Exam, Vital Signs, ECOG PS, Hematology and Serum Chemistry visit days have a - 3 day window during Cycles 2 through 6.

³ Treatment Administration +/- 7 day window. Physical Exam, Vital Signs, ECOG PS, Hematology and Serum Chemistry visit days have a - 7 day window for all cycles after cycle 6.

⁴ To include assessment of B-symptoms

⁵ Unilateral bone marrow aspirate and/or biopsy should be completed within 90 days prior to Day 1 of Cycle 1 as clinically indicated per standard of care. In addition, a post-baseline bone marrow biopsy should be completed to confirm potential CR by radiological assessment.

⁶ Scans should be completed within 30 days prior to Day 1 of Cycle 1. All tumor evaluations have a +/- 7 day window. Radiology assessment should include FDG-PET and/or a contrast enhanced CT scan of chest, abdomen, and pelvis. If iodinated contrast is contraindicated, a non-contrast chest CT coupled with a gadolinium-enhanced MRI of the abdomen/pelvis is an acceptable substitute. For Waldenstrom's macroglobulinemia evaluation should include immunofixation and serum electrophoresis. For patients with WM without nodal involvement, response will be assessed by quantitative monoclonal IgM protein every 3 cycles

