8.6 EVALUATION OF BEST OVERALL RESPONSE

The best overall response is the best response recorded from the start of the treatment until disease progression/recurrence (taking as reference for progressive disease the smallest measurements recorded since the treatment started). The patient's best response assignment will depend on the achievement of both measurement and confirmation criteria as per the NHL established criteria used in this study (See Appendix A).

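### An MZL patient followed by PET-CT whose disease was not FDG-avid at baseline and has not changed is CR in the Appendix A PET-CT column but SD under section 8.4 and the CT column, and no rule says which prevails

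*Combined protocol and SAP*

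**What the plan says.** Appendix A sets out the lymphoma response criteria in two columns, PET-CT-based and CT-based.

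- **PET-CT column.** CR at nodes and extra-lymphatic sites is "Score 1, 2, or 3* with or without a residual mass on 5PS". Non-measured lesions and organ enlargement do not apply to a PET-CT CR. PR needs a score of 4 or 5 "with reduced uptake compared with baseline and residual mass(es) of any size". SD is "Score 4 or 5 with no significant change in FDG uptake from baseline at interim or end of treatment". PD at existing sites needs a score of 4 or 5 with rising uptake; otherwise it needs new avid foci. The scale note begins "1, no uptake above background", so a lesion that never took up tracer scores 1.
- **CT column.** For CR, "Target nodes/nodal masses must regress to" 1.5 cm or less in longest diameter.

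The modality is left open. Footnote 6 of the section 5.1 schedule says "Radiology assessment should include FDG-PET and/or a contrast enhanced CT scan of chest, abdomen, and pelvis". Section 8.1 prefers CT but permits PET-CT where it is the investigator's standard of care. Entry (section 3.1, criterion 3) is a size rule: "At least 1 measurable disease lesion >1.5 cm in at least one diameter by CT/CT-PET or magnetic resonance imaging (MRI").

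Two places claim to govern classification. Section 8.4 says evaluable patients are classified by the definitions that follow it (8.4.1 to 8.4.6). Section 8.6 says best response is assigned "as per the NHL established criteria used in this study (See Appendix A").

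**The concern.** A low score on the five-point scale shows that treatment worked only if the score was high beforehand. A patient who starts with a low score can meet the PET-CT definition of CR with no change in disease. The same-technique rule in section 8.1 does not prevent this, because PET at both visits is exactly what produces it.

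The primary outcome for MZL is the percentage with CR or PR (section 9.10.1), and the CR rate is secondary (section 9.10.2). The trial has one arm, so a misclassified patient goes straight into the reported rate. That patient also enters the DOR set, where the recorded duration would be the time an untouched indolent lymphoma took to progress.

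**Working it through.** The plan states no figure on this point. The check is a side-by-side reading, followed by the effect of one patient.

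**Step 1. One assumed patient, both routes.** Take an MZL patient with a 3 cm node scoring 2 at baseline. After cycle 3 the node is the same size and scores 2. There are no new lesions.

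| Category | Appendix A, PET-CT column | Section 8.4 | Appendix A, CT column |
|---|---|---|---|
| CR | Met: score 1 to 3, residual mass allowed | Not met: 8.4.1 wants all evidence of disease gone | Not met: 3 cm exceeds 1.5 cm |
| PR | Not met: needs 4 or 5 | Not met: 8.4.3 wants SPD down by at least 50%; change is 0% | Not met: same SPD rule |
| SD | Not met: needs 4 or 5 | Met: 8.4.5, neither CR/PR nor PD | Met: SPD fall below 50%, no PD |
| PD | Not met: no rise to 4 or 5, no new avid focus | Not met | Not met |

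The result is CR by one route and SD by the other two.

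The same happens in splenic MZL without lymphadenopathy, where section 8.5 makes the spleen the index lesion. A non-avid spleen that stays enlarged passes the PET-CT CR cells, while 8.4.1 requires normal size.

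**Step 2. Is there a baseline-avidity condition elsewhere?** Sections 3.1, 5.1 (footnote 6), 8, 8.1, 8.3, 8.5 and 8.6 contain none.

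**Step 3. Is there a precedence rule?** Sections 8.4 and 8.6 point to different definitions, and neither yields to the other. Section 8.4.5 cannot settle it: it makes SD depend on not having attained CR, and the definition of CR is what is in dispute.

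**Step 4. Size per patient.** The synopsis allows up to 20 MZL and up to 20 WM patients.

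- MZL: 1/20 = 5.0 percentage points per patient.
- Both histologies combined: 1/40 = 2.5 points per patient.

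The counts below are assumed for illustration. Intervals are exact (Clopper-Pearson) 95%, because the plan names no method: lower limit = 0.025 quantile of Beta(x, n−x+1), upper limit = 0.975 quantile of Beta(x+1, n−x), with n = 20.

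| Patients coded CR instead of SD | MZL ORR (95% CI) | MZL CR rate (95% CI) |
|---|---|---|
| 0 | 10/20 = 50% (27.2 to 72.8) | 0/20 = 0% (0 to 16.8) |
| 1 | 11/20 = 55% (31.5 to 76.9) | 1/20 = 5% (0.1 to 24.9) |
| 2 | 12/20 = 60% (36.1 to 80.9) | 2/20 = 10% (1.2 to 31.7) |
| 3 | 13/20 = 65% (40.8 to 84.6) | 3/20 = 15% (3.2 to 37.9) |

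**Step 5. Marrow.** Section 5.2.1 asks patients with baseline marrow involvement for a biopsy to confirm a radiological CR. If that biopsy is not done, 8.4.3 turns the clinical CR into PR. The CR rate is then not raised, but the ORR still is.

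**The case against.** The strongest reply is that the protocol body already gives the right answer. Section 8.4 classifies by its own definitions, and under those an unchanged 3 cm node is neither CR nor PR and so is SD. The restriction to CT-only disease in 8.4.5 sits in its second sentence; the first covers PET-assessed patients too. CT is the preferred method, SPD is recorded at baseline as the reference for regression, and the CT column rejects the patient. The PET-CT column's talk of a residual mass and of sites of initial involvement also presupposes that something responded. The cited classification may itself limit PET to avid disease, but that cannot be checked from these documents.

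Most of this stands. A reader might infer from the PET-CT column that such a patient definitely counts as a complete responder and cannot be SD. The documents do not support that: it follows only if the column is applied alone, and nothing says that it is.

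The reply does not remove the conflict. Section 8.6 sends best response to Appendix A, a preference for CT does not bar PET, and neither place is given precedence. Two careful readers could code the same unchanged patient differently. The marrow biopsy does not help, since it does not test an unchanged node or spleen.

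**Conclusion.** The point holds as an unresolved conflict over the primary MZL endpoint. For unchanged disease that was not avid at baseline and is followed by PET-CT, one stated criterion gives CR, others give SD, and nothing decides between them. It is chiefly an MZL matter, because WM response turns mainly on IgM.

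Each patient coded CR instead of SD adds 5 points to the MZL ORR at n = 20 and joins the DOR set. The CR rate rises by the same amount unless an involved marrow goes unassessed. This assumes full MZL enrolment with all 20 patients in the mITT population, and that every involved site in the patient scored 1 to 3.

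A reader might want to go further and estimate how many patients are affected. The documents give neither the share of MZL that is non-avid nor the share followed by PET, so any such range would be assumption alone. The number could be zero.

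The shifts are small beside the width of the intervals, and section 9.11 says no formal claims will be made. The change should still be made: the ambiguity sits on the primary endpoint, can only push the rate upwards, and is cheap to remove.

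**What to change.** Make three changes in Appendix A, section 8.1 and the SAP, which section 9 requires to be final before database lock.

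1. The PET-CT column applies only to patients with a baseline FDG-PET within 30 days before Cycle 1 Day 1 on which at least one index lesion scored 4 or 5. All other MZL patients are assessed by the CT-based column.
2. In a PET-assessed patient, any involved site that scored 1 to 3 at baseline must also meet the CT-based criterion before overall CR is assigned.
3. State whether section 8.4 or Appendix A governs where they differ.

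The cost is a few sentences. The 30-day window already applies to baseline scans, the CT column already exists, and CT is already the preferred method. Patients without a baseline PET are assessed by CT measurements. The ORR and CR rate may come out slightly lower.
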